CLINICAL STUDY PROTOCOL

TITLE: A Single-center, Retrospective Study to Evaluate the Clinical Performance of Artificial Intelligence Medical Assisted Diagnostic Software (VeriSee AMD) for Screening of Age-Related Macular Degeneration

Protocol Number: AHCI21001

Phase of Study: Pivotal study

Version No: 1.2

Version Date: 16-Jul-2021

Sponsor: Acer Medical Inc.

Sponsor Address: [name]

Confidentiality Statement

The information in this document contains trade secrets and commercial information that are privileged or confidential and may not be disclosed unless such disclosure is required by applicable laws and regulations. In any event, persons for whom this information is disclosed must be informed that the information is privileged or confidential and may not be further disclosed by them. These restrictions on disclosure will apply equally to all future information supplied to you that is indicated as privileged or confidential.

Clinical Study Protocol

Title:

A Single-center, Retrospective Study to Evaluate the Clinical Performance of Artificial Intelligence Medical Assisted Diagnostic Software (VeriSee AMD) for Screening of Age-Related Macular Degeneration.

Objectives:

This study is to evaluate the clinical performance of VeriSee AMD for AMD screening from color fundus photography images. The sensitivity and specificity of VeriSee AMD's automated image analysis for screening the age-related macular degeneration will be determined.

Investigational product:

1. Name: VeriSee AMD
2. Model: AMD-01
3. Manufacturer: Acer Medical Inc.
4. Method of analysis: VeriSee AMD is a software as medical device that incorporates an artificial intelligence (AI)-based algorithm to evaluate the age-related macular degeneration (AMD) from color fundus photography images screening. The screening result of AMD will be determined as non-more than level 3 AMD (non-mtl3AMD) or more than level 3 AMD (mtl3AMD).
5. Intended use: VeriSee AMD is intended to screen AMD from the images taken by color fundus photography, which can assist the physicians to assess whether further examination for retinopathy by the ophthalmologist is needed. The screening result of AMD will be determined as non-mtl3AMD or mtl3AMD. VeriSee AMD only provides the screening results of AMD for the physicians' reference and VeriSee AMD is not intended to diagnose of AMD, detect concomitant diseases, or treat AMD.
6. Device type: Software as a medical device (SaMD)

Clinical Study Protocol

Endpoints:**1. Primary endpoint:**

- To evaluate the clinical performance of VeriSee AMD by determining the sensitivity and specificity.

2. Secondary endpoints:

- To evaluate the clinical performance of VeriSee AMD by determining the positive and negative predictive values (PPV and NPV)
- To determine the percentage of subjects' images with insufficient quality as judged by VeriSee AMD

Selection criteria:

The screening by inclusion and exclusion criteria for eligibility of subjects will be performed by the information technology office at the clinical site. A dedicated ophthalmologist will be responsible to confirm the eligibility of enrolled subjects' color fundus photography images for inclusion criterion # 3 and exclusion criterion # 2.

1. Main inclusion criteria:

(1) Subject with age \geq 50 years old

(2) Subject with image taken by Canon CR-2 that meet the following requirement:

- The resolution of image is 271 \times 271 pixels or higher.
- The angle view of image is 45 or 50 degrees.

(3) Subject's image includes macula as judged by the ophthalmologist.

2. Main exclusion criteria:

(1) The color fundus photography image previously used by VeriSee AMD during the development process and pre-clinical test

(2) The macula or other part in the image of color fundus photography is unclear to determine the disease condition as judged by the ophthalmologist.

Clinical Study Protocol**Study procedures:**

This is a single-center, retrospective study to evaluate the performance of VeriSee AMD for screening of potential age-related macular degeneration (AMD). The sensitivity and specificity of VeriSee AMD will be determined in this study by comparing the results of gold standard, which is the judgment of AMD by the ophthalmologists (evaluators).

Age-Related Macular Degeneration Severity Scale (AMD Severity Scale)	
AMD Level	Criteria
1	Drusen maximum size < circle C-0 (63 µm diameter) and total area < circle C-1 (125 µm diameter)
2	
Presence of one or more of the following:
 
 (a) Drusen maximum size \geq circle C-0 but < circle C-1 (b) Drusen total area \geq circle C-1 (c) Retinal pigment epithelial pigment abnormalities consistent with AMD, defined as one or more of the following in the central or inner subfields: 
 (1) Depigmentation present (2) Increased pigment \geq circle C-1 (3) Increased pigment present and depigmentation at least questionable
3	
Presence of one or more of the following:
 
 (a) Drusen maximum size \geq circle C-1 (b) Drusen maximum size \geq circle C-0 and total area $>$ circle I-2 and type is soft indistinct (c) Drusen maximum size \geq circle C-0 and total area $>$ circle O-2 and type is soft distinct (d) Geographic atrophy within grid but none at center of macula
4 (Advanced)	
Presence of one or more of the following:
 
 (a) Geographic atrophy in central subfield with at least questionable involvement of center of macula (b) Evidence of neovascular AMD 
 (1) Fibrovascular/serous pigment epithelial detachment (2) Serous (or hemorrhagic) sensory retinal detachment (3) Subretinal/subretinal pigment epithelial hemorrhage (4) Subretinal fibrous tissue (or fibrin) (5) Photocoagulation for AMD

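### Could the software's positive class and the ophthalmologists' gold standard be split at different AMD levels?

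*Protocol*

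**What the plan says.** Item 4 (Method of analysis) under Investigational product in the Protocol defines the output: "The screening result of AMD will be determined as non-more than level 3 AMD (non-mtl3AMD) or more than level 3 AMD (mtl3AMD". Item 5 (Intended use) repeats the two labels and adds no level numbers: "The screening result of AMD will be determined as non-mtl3AMD or mtl3AMD".

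The primary endpoint is "To evaluate the clinical performance of VeriSee AMD by determining the sensitivity and specificity". The first secondary endpoint covers the predictive values. Neither bullet restates the positive class.

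Study procedures says that sensitivity and specificity are obtained "by comparing the results of gold standard, which is the judgment of AMD by the ophthalmologists (evaluators". The table headed "Age-Related Macular Degeneration Severity Scale (AMD Severity Scale" follows directly. It has levels 1 to 4, and level 4 is marked as advanced. The text available for this review ends with the last row of that table.

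**The concern.** Two features prompt the question. First, on a scale that stops at 4, more than level 3 means level 4 alone if taken literally. Level 3, which includes large drusen and geographic atrophy away from the centre, is then negative. A reader might wonder whether level 3 and above was meant. Second, the gold-standard sentence gives no level. Taken in isolation, a judgment of AMD could mean level 4, level 3 and above, or any AMD.

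If the two sides were cut differently, the levels between the cuts would become systematic errors in the primary 2x2 table. They would be false positives where the software's cut is the lower one and false negatives where it is the higher one. PPV and NPV come from the same table and would shift with it. In a pivotal study whose primary endpoint is sensitivity and specificity, that deserves a check.

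**Working it through.** The Protocol text shown gives no sample size, performance goal or level distribution, so there is no planned figure to reproduce. The check is first one of reading, then a conditional calculation.

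**1. Reading the sections together**

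| Element | Place in the Protocol | Cut stated |
|---|---|---|
| Software output | Investigational product, item 4 | more than level 3 against the rest |
| Same, restated | Investigational product, item 5 | same two labels |
| Sensitivity, specificity | Endpoints, primary | none; refers to the software |
| PPV, NPV | Endpoints, secondary | none; refers to the software |
| Gold standard | Study procedures | none; severity scale follows at once |
| Levels | Severity scale table | 1, 2, 3, 4 |

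Only one split appears anywhere. A contradiction would need a second one, such as a sentence counting level 3 as positive or a rule that evaluators record any AMD. Neither is there. The word level in the software's class names is given meaning only by the table, and the table is attached to the evaluators' judgment. The natural reading is that evaluators grade on the scale and the grades are sorted into the two named classes.

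**2. Matching cuts**

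Take software that makes no errors at its own cut *c*, and let reference-positive also mean level at or above *c*. Every reference-positive image is flagged and every reference-negative image is not, so sensitivity = specificity = 100% for any mix of levels. This holds for *c* = 4 and for *c* = 3. Whether the label is literal or loose therefore creates no bias, provided one cut serves both sides.

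**3. Mismatched cuts (all inputs assumed)**

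Assume shares of 85% levels 1-2, 10% level 3 and 5% level 4, with sensitivity and specificity of 0.90 at the software's own cut.

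- Software at level 3 and above, reference level 4 only: specificity = (0.85 × 0.9 + 0.10 × 0.1) / 0.95 = 0.775 / 0.95 = 0.816.
- Software at level 4, reference level 3 and above: sensitivity = (0.05 × 0.9 + 0.10 × 0.1) / 0.15 = 0.055 / 0.15 = 0.367.

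Ranges:
- The specificity runs from 0.884 (2% level 3, 1% level 4) to 0.722 (20%, 10%).
- The sensitivity depends only on the ratio *r* of level 3 to level 4, as (0.9 + 0.1*r*) / (1 + *r*). It is 0.633 at *r* = 0.5 and 0.260 at *r* = 4.

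**4. The any-AMD reading**

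This is the alternative closest to the gold-standard wording. Take any AMD as level 2 and above, with error-free software and assumed shares of 20% level 2, 10% level 3 and 5% level 4.

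- Software at level 4: sensitivity = 0.05 / 0.35 = 0.143.
- Software at level 3 and above: sensitivity = 0.15 / 0.35 = 0.429.

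Over four assumed mixes (level 2 at 10-20%, level 3 at 5-20%, level 4 at 2-5%) the ranges are 6-25% and 38-56%. Values this low come from scoring the software on a target it is not described as detecting, which is a reason to doubt that this reading was intended.

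**The case for a change.** The best case for a change is that the target condition is not an analysis detail. It decides what sensitivity and specificity mean and how evaluators work, and it normally belongs in the protocol. This Protocol already defines the software's classes, the gold standard and the scale, so it could be expected to join them. The repair would cost a sentence and no data. If a mapping rule after the table did count level 3 as positive, it would clash with the literal label in item 4.

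Some of this stands. The reference-positive class does belong in a protocol, the sections shown do not spell it out, and the label is awkward on a scale with one level above 3. The arithmetic on what a mismatch would do is also right.

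The rest does not carry. The argument rests on an unwritten link, not on two statements that conflict. The available text stops at the table, just where a grading and dichotomisation rule would naturally come, so its absence cannot be asserted. Taken literally, the label is a complete and usable definition, and nothing in the document shows it to be wrong. The possible clash over level 3 is conjecture about text not shown.

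**Conclusion.** No change to the plan follows. This is a gap that analysts fill sensibly: the evaluators' grades on the printed scale are sorted into the same two classes that the software reports. With that done, sensitivity, specificity, PPV and NPV carry no distortion from the cut, whichever level the label denotes.

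The size of the problem on the document as it stands is therefore nil. The figures of 0.816 and 0.367 against 0.90, and the lower ones for an any-AMD reference, measure a mismatch that the document does not state, using level shares and an accuracy it does not give.

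The conclusion rests on two assumptions: that evaluators grade on the scale placed after the gold-standard sentence, and that no text after the table sets a different split. A sentence giving the reference another cut would reopen the question. This review takes no position on which levels ought to count as positive.

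### Are PPV and NPV a faulty secondary endpoint because mtl3AMD may be more or less common in the sample than in screening?

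*Protocol*

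**What the plan says.** Three parts of the protocol bear on this point.

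- **Endpoints.** The primary endpoint is "To evaluate the clinical performance of VeriSee AMD by determining the sensitivity and specificity". The first secondary endpoint evaluates performance "by determining the positive and negative predictive values (PPV and NPV"). In the text shown, neither carries a formula, a numerical target, a reference prevalence or a success criterion.
- **Investigational product, 5. Intended use.** "VeriSee AMD is intended to screen AMD from the images taken by color fundus photography". The result is meant to help a physician decide whether to send the person on to an eye specialist. The output is binary: "The screening result of AMD will be determined as non-mtl3AMD or mtl3AMD".
- **Study procedures and Selection criteria.** The design is described thus: "This is a single-center, retrospective study to evaluate the performance of VeriSee AMD for screening of potential age-related macular degeneration (AMD"). The main inclusion criteria are a minimum age of 50 years, an image from one camera model with set resolution and field angle, and a macula within the image. The main exclusions are images already used in development or pre-clinical testing, and images for which "The macula or other part in the image of color fundus photography is unclear to determine the disease condition as judged by the ophthalmologist".

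**The concern.** A physician who acts on a screening result wants to know how likely disease is after a positive result and how safe a negative one is. PPV and NPV answer this, but only at the prevalence of the group in which they were calculated. Here that group is one center's archive. Only the age limit describes a population; the other criteria describe images.

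If mtl3AMD were more common in the archive than among people screened, the sample PPV would be too high and the sample NPV too low for the stated use; if it were less common, the reverse. A pivotal study could then report predictive values that do not apply to screening. The definitions of sensitivity and specificity do not depend on prevalence in this way, so only the secondary endpoint is in question.

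**Working it through.** **Inputs.** The document gives no sample size, prevalence, or target sensitivity or specificity, so there is no figure of the plan's own to reproduce. All values of sensitivity (Se), specificity (Sp) and prevalence (p) below are assumptions.

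**Step 1: does prevalence matter?** Yes.

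PPV = Se·p / [Se·p + (1−Sp)(1−p)]; NPV = Sp(1−p) / [Sp(1−p) + (1−Se)p].

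With Se = Sp = 0.90:

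| p | PPV | NPV |
|---|---|---|
| 30% | 0.27/(0.27+0.07) = 0.794 | 0.63/(0.63+0.03) = 0.955 |
| 10% | 0.09/(0.09+0.09) = 0.500 | 0.81/(0.81+0.01) = 0.988 |

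In odds form, odds(PPV) = LR+ × p/(1−p), where LR+ = Se/(1−Sp). If Se and Sp carry over, the PPV odds at two prevalences differ by the ratio of the prevalence odds, whatever the accuracy. For 30% against 10% the ratio is 0.4286/0.1111 = 3.86; for 15% against 10% it is 0.1765/0.1111 = 1.59; for equal prevalences it is 1.00.

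**Step 2: does the document show that the prevalences differ?** No.

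| Criterion | Selects on | Selects on AMD status? |
|---|---|---|
| Age 50 or older | Person | No |
| Camera, resolution, angle | Image | No |
| Macula in image | Image | No |
| Not used in development or pre-clinical testing | Image history | No |
| Not too unclear to judge | Image quality | No |

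Nothing fixes a ratio of cases to non-cases, the design in which a sample PPV would most plainly mislead. This does not prove that the prevalences agree: age or image clarity may be associated with disease, and an archive may differ from a screening program. But the text gives neither the direction nor the size of any gap. The lists cover the main criteria and the text available ends at the severity scale, so a sampling rule may stand elsewhere.

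The assumed 10% to 30% cannot be tied to the document either. Prevalence depends on which levels count as positive; read literally, a category above level 3 contains only level 4.

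**Step 3: what is lost if only sample ratios are reported?** Nothing that the reported results cannot restore. Suppose the sample has 30% prevalence with Se = Sp = 0.90, so that its PPV is 0.794. The primary endpoint gives LR+ = 0.90/0.10 = 9. At 10% prevalence, odds(PPV) = 9 × 0.1111 = 1.00, so PPV = 0.500. At 5%, odds = 9 × 0.0526 = 0.474, so PPV = 0.474/1.474 = 0.321. Values at set prevalences are functions of p and the two primary estimates, and they use no further study data.

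**Step 4: would values at set prevalences settle the matter?** Only if Se and Sp carry over to screening. At p = 10% and Se = 0.90:

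- Sp 0.90: PPV = 0.500
- Sp 0.85: PPV = 0.09/(0.09+0.135) = 0.400
- Sp 0.80: PPV = 0.09/(0.09+0.18) = 0.333

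Such a table trades one assumption for another, and its prevalences would have to come from outside the study.

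**The case for a change.** The strongest opposing case does not allege an omission. The protocol itself makes PPV and NPV a measure of clinical performance for a screening product, so it should make them speak to screening. With the accuracy assumed above, the same device could appear to have about four in five positives correct, or one in two. Two sentences and one table would avoid misreading, without new study data. Fixing the prevalences before analysis would stop anyone from choosing flattering ones afterwards.

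Part of this stands. A sample PPV or NPV should be read together with the sample's prevalence, and if values at other prevalences are presented, setting those prevalences in advance is good practice.

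It still identifies no fault in the protocol. Naming PPV and NPV as endpoints does not commit the sponsor to any formula, or to presenting sample ratios as screening values. How they are calculated, labelled and standardised is ordinary content for the statistical analysis plan, which may already provide for it. The same remark could be made about any diagnostic accuracy study that reports predictive values. No hypothesis or decision in the text shown rests on PPV or NPV, so the addition would change no stated result.

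**Conclusion.** The concern does not hold. That predictive values vary with prevalence is true and can be large: a factor of 3.86 in PPV odds under assumed prevalences of 30% and 10%. The document, however, supplies neither prevalence, and the factor is 1.00 if the two agree. No passage is wrong, contradicts another or fixes a poor choice on this point. Carried out as written, the plan gives PPV and NPV that are valid for the sample, beside sensitivity and specificity as the primary endpoint.

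This conclusion rests on two points: the calculation of PPV and NPV may properly be left to the statistical analysis plan, and the visible criteria contain no selection on AMD status. It would need another look if a sampling rule elsewhere fixed the mix of cases and non-cases and the resulting PPV or NPV were then put forward as values for screening.

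### The insufficient-quality endpoint appears to be measured only after an ophthalmologist has removed the unclear images

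*Protocol*

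**What the plan says.** Image clarity appears in two roles in the Protocol.

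- **As an outcome.** Under Endpoints, the second of the secondary endpoints is "To determine the percentage of subjects' images with insufficient quality as judged by VeriSee AMD". Here the software decides. No denominator is given.
- **As an eligibility rule.** Under Selection criteria, main exclusion criterion (2) reads "The macula or other part in the image of color fundus photography is unclear to determine the disease condition as judged by the ophthalmologist". Here a person decides.

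The opening paragraph of Selection criteria divides the eligibility work: "The screening by inclusion and exclusion criteria for eligibility of subjects will be performed by the information technology office at the clinical site". Two image-level checks are left to one ophthalmologist, who is to "confirm the eligibility of enrolled subjects' color fundus photography images for inclusion criterion # 3 and exclusion criterion # 2". Inclusion criterion (3) is a field-of-view rule: "Subject's image includes macula as judged by the ophthalmologist".

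The intended use, under Investigational product, item 5, is that "VeriSee AMD is intended to screen AMD from the images taken by color fundus photography", so as to help physicians judge whether a patient needs to see an ophthalmologist. It describes no ophthalmologist's clarity check ahead of the software.

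**The concern.** An image that fails an exclusion criterion is ordinarily outside the study. If that holds here, the images an ophthalmologist could not read have gone before the software's rejection rate is computed. These are the images a quality check would be expected to reject most often. What remains is the software's rejection rate given that an ophthalmologist has already found the image clear.

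In the intended use the software comes before the ophthalmologist. A user wants to know how often it will return no result on macula images that no ophthalmologist has sorted first, and the endpoint as naturally read does not say. A low percentage could be taken as that figure when it is not.

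The reason for excluding ungradable images applies to sensitivity and specificity, which need a reference grade. It does not apply to this endpoint, which needs only the software's own output.

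**Working it through.** The Protocol states no expected rejection rate and no share of unclear images, so there is no figure of its own to reproduce. The check has two parts.

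**1. Which images are counted**

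- Clarity is listed as an exclusion criterion, and the ophthalmologist's task is described as confirming eligibility. This points to a denominator of images that passed.
- The endpoint refers only to images of subjects, and the ophthalmologist's check is on images of subjects called enrolled. This leaves room for a denominator in which unclear images of enrolled subjects still count.
- The text does not say that the software is run on images excluded as unclear.

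The first reading is the more natural one, but the wording does not settle it.

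**2. What the first reading does to the percentage**

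Among macula-containing images, all three inputs are assumptions:

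- e = share excluded as unclear, 2% to 15%
- a = software rejection rate among the excluded, 20% to 80%
- b = software rejection rate among the kept, 2% to 5%

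Then:

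- endpoint on eligible images = b
- rate before exclusion criterion 2 = e·a + (1 − e)·b = b + e(a − b)
- gap = e(a − b)

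| Quantity | e | a | b | Calculation | Result |
|---|---|---|---|---|---|
| Lowest rate before exclusion | 0.02 | 0.20 | 0.02 | 0.02 + 0.02 × 0.18 | 2.36% |
| Highest rate before exclusion | 0.15 | 0.80 | 0.05 | 0.05 + 0.15 × 0.75 | 16.25% |
| Smallest gap | 0.02 | 0.20 | 0.05 | 0.02 × 0.15 | 0.3 points |
| Largest gap | 0.15 | 0.80 | 0.02 | 0.15 × 0.78 | 11.7 points |

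Throughout this range the endpoint itself reports only 2% to 5%.

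Worked example, 1000 macula-containing images, e = 5%, a = 50%, b = 2%:

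- kept: 950, of which 0.02 × 950 = 19 rejected; reported 19/950 = 2.0%
- excluded: 50, of which 0.50 × 50 = 25 rejected
- before exclusion: (19 + 25)/1000 = 44/1000 = 4.4%
- share of rejections that the endpoint does not see: 25/44 = 57%

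If a = b the gap is zero, and if a < b its sign reverses.

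Images without the macula raise a different question and would blur the headline. Adding 100 of them to the example gives 44/1100 = 4.0% if the software rejects none and 144/1100 = 13.1% if it rejects all.

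**The case against.** The strongest reply is that the Protocol does not fix what is being criticised. It names a percentage and leaves the denominator open, and a statistical analysis plan that is not shown could define it. The reference to enrolled subjects can be read as placing enrolment before the clarity check, in which case unclear images still count and there is no gap. The conditional rate is also defensible in itself: it isolates failures attributable to the software and uses the same images as sensitivity and specificity. The two clarity judgements need not coincide, because the software's quality criteria are not shown. The assumed range takes a > b throughout, so a positive gap is built in.

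Much of this stands. The reading is not certain, the size is unknown, the direction depends on a > b, and nothing in the Protocol is contradictory or miscalculated. Even the rate before exclusion would describe one centre and one camera model.

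The point about the analysis plan does not dispose of the matter. Whether images that fail exclusion criterion 2 are kept and run through the software is a matter of eligibility and data collection, which a protocol fixes. A later definition of the denominator cannot recover output that was never generated. Nor does the case for the conditional rate tell against reporting both rates, since the conditional one then remains visible.

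**Conclusion.** The concern holds as a cheap improvement to a descriptive secondary endpoint, with medium confidence because it rests on the more natural of two possible readings. On that reading the percentage describes software rejection among ophthalmologist-gradable images, which is less informative for the stated screening use than the rate before exclusion criterion 2. It understates that rate if the software rejects unclear images more often than clear ones, which is plausible but not documented. The range of 0.3 to 11.7 points shows only that the gap could be negligible or large; it is no estimate for this study. Inclusion criterion 3 is not part of the criticism.

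**What to change.** In the Protocol:

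1. State the denominator of the insufficient-quality endpoint.
2. Run VeriSee AMD on all images that meet inclusion criteria 1 and 2 and are not removed by exclusion criterion 1 ("The color fundus photography image previously used by VeriSee AMD during the development process and pre-clinical test").
3. Compute the endpoint on the macula-containing images before exclusion criterion 2 is applied, and show it separately for images the ophthalmologist kept and those excluded as unclear.
4. Report images without the macula in a separate row, outside the headline rate, and give the numbers removed under inclusion criterion 3 and under exclusion criterion 2.
5. Keep sensitivity and specificity on ophthalmologist-gradable images, and say so.

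The cost is a change of wording and a little extra software processing. The Protocol says "This is a single-center, retrospective study to evaluate the performance of VeriSee AMD", so the images already exist, and the excluded ones need no reference grading. The one drawback for the sponsor is that the headline percentage may look less favourable.

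### Does the 271 x 271 pixel eligibility floor make the drusen-based reference grade unworkable?

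*Protocol*

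**What the plan says.** Under Selection criteria, main inclusion criterion 2 begins "Subject with image taken by Canon CR-2 that meet the following requirement" and sets two conditions: a resolution of 271 by "271 pixels or higher", and "The angle view of image is 45 or 50 degrees". Main exclusion criterion 2 removes an image if the macula or another part of it "is unclear to determine the disease condition as judged by the ophthalmologist". A dedicated ophthalmologist confirms that criterion and the one requiring the macula to be in the picture. The information technology office screens for eligibility.

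Under Study procedures, the comparator is the "gold standard, which is the judgment of AMD by the ophthalmologists (evaluators". The AMD Severity Scale in the same section starts level 1 with "Drusen maximum size < circle C-0" and gives the two circles as "circle C-0 (63 µm diameter" and "circle C-1 (125 µm diameter". Level 3(a) turns on the larger circle, and 3(b) and 3(c) use the smaller one together with drusen area and type. Level 3(d) and all of level 4 are defined by geographic atrophy or neovascular signs.

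The device output, described under Investigational product, is binary: above level 3 (mtl3AMD) or not.

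**The concern.** The eligibility floor and the measuring scale stand in the same protocol, and the text at hand does not relate one to the other. If a 45 or 50 degree field is spread over only 271 pixels, one pixel covers roughly as much retina as the smaller circle and a third to a half of the larger one. A grader working from such an image could not reliably tell a druse just under 125 µm from one just over it.

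Sensitivity and specificity are the primary endpoint of a study labelled pivotal, and both are computed against this reference grade. If enough images were that coarse, errors in the reference would pass directly into both estimates. Exclusion criterion 2 is a matter of judgment and sets no pixel limit, so it does not obviously close the gap.

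**Working it through.** The protocol states no pixel scale, so there is no figure of its own to reproduce.

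**Inputs from the protocol:** 271 pixels; 45 or 50 degrees; circles C-0 = 63 µm and C-1 = 125 µm.

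**Assumptions, not in the protocol:** k = 250 to 320 µm of retina per degree, with the field filling the full image width.

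**Formulas:** µm per pixel = degrees × k / 271; pixels across a circle = diameter / (µm per pixel).

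| Field | k | µm per pixel | C-0 in pixels | C-1 in pixels |
|---|---|---|---|---|
| 45° | 250 | 45 × 250 / 271 = 41.5 | 63 / 41.5 = 1.52 | 125 / 41.5 = 3.01 |
| 45° | 320 | 45 × 320 / 271 = 53.1 | 1.19 | 2.35 |
| 50° | 250 | 50 × 250 / 271 = 46.1 | 1.37 | 2.71 |
| 50° | 320 | 50 × 320 / 271 = 59.0 | 1.07 | 2.12 |

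One pixel is thus 33% (1 / 3.01) to 47% (1 / 2.12) of the C-1 diameter. The result does not hinge on k. For C-1 to span even 5 pixels at 45 degrees, k would have to be (125 / 5) × 271 / 45 = about 151 µm per degree, far below the range used.

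**Which grades are exposed.** A one-pixel error matters at the level 2/3 cut only for drusen within one pixel of 125 µm. That is 125 ± 41.5, or 83.5 to 166.5 µm, at the fine end, and 125 ± 59.0, or 66 to 184 µm, at the coarse end. Larger or smaller drusen stay on the right side of this cut. Levels 3(d) and 4 do not depend on either circle.

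**What must hold for this to reach sensitivity and specificity:**

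1. Some images must lie near 271 pixels. The protocol gives neither the camera's native resolution nor the archived one, so this share is unknown and may be zero.
2. The ophthalmologist applying exclusion criterion 2 must let those images through.
3. The positive class must include level 3. Read literally, above level 3 is level 4 against levels 1 to 3, and an error at the 1/2 or 2/3 boundary does not change the class. If level 3 or above is meant, C-1 becomes one deciding threshold, and C-0 enters only through 3(b) and 3(c).

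The document establishes none of the three.

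**A higher floor.** Requiring C-0 to span 5 pixels, for example, would need 5 × 45 × 250 / 63 = 893 to 5 × 50 × 320 / 63 = 1,270 pixels across the field. The target of 5 has no basis in the protocol.

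**The case for a change.** The strongest case for a change is that the mismatch is real, survives every plausible value of k, and is fixed in the protocol itself rather than left to an analysis plan. The resolution rule is not among the criteria the ophthalmologist is assigned to confirm. If exclusion criterion 2 really removed every coarse image, the stated floor would do nothing. On that view, two lines would settle the matter: one justifying 271 pixels against the circles, and one saying that evaluators grade the original camera file.

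The arithmetic stands, and so does the remark that the floor is not justified against the scale. The consequence does not. An image too coarse to grade is just what exclusion criterion 2 describes, and the reference standard is itself ophthalmologists' judgment, so calling the check subjective does not show that it fails.

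A line on grading from the original file would only record a practice that the available text never contradicts; that text stops at the severity table and does not show how evaluators view the images. A floor near 1,000 pixels has a cost: if the device accepts smaller images, the study would no longer test it on them, and images archived only at reduced size would be lost.

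**Conclusion.** No change is needed. At the permitted minimum, and assuming 250 to 320 µm of retina per degree, the 63 µm circle spans about 1.1 to 1.5 pixels and the 125 µm circle about 2.1 to 3.0, so drusen close to either cut would be barely resolved. It does not follow that the reference grade cannot be assigned, or that sensitivity and specificity are biased. That would need images near the floor, a failure of the ophthalmologist's exclusion, and a positive class that includes level 3, and the protocol shows none of these. The pixel figures measure resolution, not bias; the bias has no demonstrable size.

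Where to set the floor is a fair trade-off between image detail and the range of images on which the device is tested. A sentence on the resolution used for reference grading would be a harmless clarification, with no demonstrated effect on the results.
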